7.1 Sample Size Determination

See section 7.2

7.2 Statistical Methods

We have a dedicated statistician for this clinical trial ([name], PhD). Our inclusion criteria use a baseline SD of systolic blood pressure variability ≥15 mmHg (2 SD above our age-matched control data [8.7±3 mmHg]). The mean coefficient of variation in 24-h BP readings in patients with FD is 19.1±5 and 99% of FD patients meet the inclusion criteria. Preliminary data shows that treatment with high dose carbidopa (600 mg/day) reduces blood pressure variability (SD of daytime SBP) by 7.0±5.5 mmHg. Power analysis for the primary outcome (reduction in SD of daytime SBP variability) is detailed in table 3. A sample size of 20 achieves 80% power to detect a reduction of 2.5 (or 2.9) from the null hypothesis of no reduction with an estimated standard deviation of 4.4 for the difference in SD at a significance level of 0.05 using a one-sided (or two-sided) one-sample t-test. The minimum detectable differences are all well below the observed reduction of BP fluctuation of 5.1 from our preliminary data. To ensure that the study is well powered, we will choose a sample size of 30 patients. To account for a drop out rate of around 15%, we will enroll 36 patients in the trial. We will examine the sample distribution of SD of daytime SBP, and if it deviates from the normal distribution, we will employ the nonparametric Wilcoxon test for robustness. In addition, to account for potential covariates, such as age, gender, and disease severity, the analysis of (co)variance (ANOVA and ANCOVA) methods will be used to model the repeated measures data.

Table 3: Power Calculation and Sample Size

Minimal detectable difference: SD BP variability high vs. low dose							
Sample size	T-test	T-test					
	One-sided	Two-sided					
20	-2.5	-2.9					
30	-2.0	-2.3					
40	-1.8	-2.0					

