This clinical trial will enroll 30 patients with FD who have excessive blood pressure variability. We will define excessive blood pressure variability as a SD of systolic blood pressure >15 mmHg or a coefficient of variation > 15% (i.e., 2 SD above our own laboratory age-matched control data) or paroxysmal hypertensive peaks >140 mmHg captured in ambulatory blood pressure recordings.

The trial will use a double-blind crossover design to evaluate the safety and efficacy of high-dose (600 mg) and low-dose (300 mg) carbidopa compared with placebo. Each treatment period will last 28-days with a 2-day dose de-escalation (Day 1: 2/3 dosage and Day 2: 1/3 dosage) and 2-day washout period between dose changes. After baseline evaluation (visit 1), enrolled patients will be randomly assigned to one of three treatment sequences (high-dose/low-dose/placebo, low-dose/placebo/high-dose or placebo/high-dose/low-dose, see Fig. 6). Study visits (in the office or via 2-way televideo conferencing with voice capabilities) will occur on the last day of each 28-day treatment period. Evaluation will include: adverse event monitoring, vital signs, safety bloods, urinalysis, 12-lead ECG, blood pressure supine and standing, orthostatic hypotension symptom severity questionnaires, autonomic testing, urinary catecholamine assay, and ambulatory blood pressure monitoring. Fig. 7 describes the timing sequence of events during the office visit.

We will monitor safety and tolerability throughout and safety bloods will be obtained after 4-weeks on each treatment arm (Aim 1). As proof of concept, we will examine the hemodynamic effects of carbidopa by measuring ambulatory BP recordings BPs supine/sitting/standing (in the office or during a telemedicine visit), and continuous BP measurements during cognitive arousal (Stroop test). We will also assess 24-h urinary catecholamine excretion (Aim 2). To learn more about the appropriate dose, we will compare 600 mg/day with 300 mg/day (Aim 3).

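### Section 7.2 does not reconcile 7.0±5.5 with the 4.4 and 5.1 used for power, enrols 36 where other sections have 30, and offers no supported calculation for high versus low dose

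*Combined protocol and SAP*

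**What the plan says.** All quotes are from section 7.2 of the combined protocol and SAP unless noted.

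- **Preliminary effect.** High-dose carbidopa "reduces blood pressure variability (SD of daytime SBP) by 7.0±5.5 mmHg".
- **What is powered.** "Power analysis for the primary outcome (reduction in SD of daytime SBP variability) is detailed in table 3". The calculation is a one-sample t-test at 0.05 with 80% power, "from the null hypothesis of no reduction with an estimated standard deviation of 4.4 for the difference in SD".
- **Benchmark.** "The minimum detectable differences are all well below the observed reduction of BP fluctuation of 5.1 from our preliminary data".
- **Counts.** "To ensure that the study is well powered, we will choose a sample size of 30 patients" and "To account for a drop out rate of around 15%, we will enroll 36 patients in the trial". The Overview in 1.4 has "This clinical trial will enroll 30 patients with FD who have excessive blood pressure variability". Section 4.3 randomises thirty. The synopsis and 1.1 give 30 without saying whether that means enrolled, randomised or completing.
- **Table 3 heading.** "Minimal detectable difference: SD BP variability high vs. low dose". Section 1.1 claims that the study is well powered both for the drug effect and for comparing the two doses.
- **Preliminary data.** Section 1.4 describes six patients with recordings before treatment and on carbidopa at 450 to 600 mg/day, with p<0.05 for the fall in daytime SD. Its text gives no size for that fall. Fig. 4, which plots it, is not shown in the copy reviewed.

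**The concern.** Section 7.2 gives one pair of numbers (7.0 and 5.5) for the reduction in SD of daytime SBP. For the same outcome it then uses another pair (5.1 and 4.4), with no source for the second. The detectable difference scales directly with the SD, so a reader cannot tell whether the 2.3 mmHg in Table 3 holds.

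The counts matter in practice. Section 8.6.1 continues the study until the target number is enrolled, and the documents give two candidates for that number. If 30 are randomised, nothing is held back for dropout after randomisation, although 7.2 itself allows for about 15%.

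The Table 3 heading invites the reader to take 2.3 mmHg as the sensitivity for high versus low dose. That comparison is Aim 3, and 1.5 says it will inform dose choice for phase III. Nothing in the preliminary data supports the figure for that contrast.

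**Working it through.** **Inputs.** SD 4.4, benchmark 5.1, alpha 0.05, 80% power, and 7.0±5.5, all from 7.2. Six preliminary patients and p<0.05, from 1.4. Dropout 15%, from 7.2.

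**Method.** Paired (one-sample) t-test: df = n−1, noncentrality = δ√n/SD, solved for the δ that gives 80% power.

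**1. Reproduce the plan (SD 4.4, one-/two-sided, mmHg).**

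| n | Recomputed | Table 3 |
|---|---|---|
| 20 | 2.54 / 2.91 | 2.5 / 2.9 |
| 30 | 2.05 / 2.33 | 2.0 / 2.3 |
| 40 | 1.76 / 2.00 | 1.8 / 2.0 |

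All six entries match. Dropout: 30/0.85 = 35.3, rounded up to 36. This also matches.

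**2. Same calculation at SD 5.5** (assuming that ± is the SD of the paired difference). n=20: 3.17/3.63. n=30: 2.56/2.91. n=40: 2.20/2.50. So Table 3 was not built on 5.5.

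**3. Can the documents show which pair is right?** With n=6, t = mean/(SD/√6):

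- 7.0 with SD 5.5: 7.0/2.245 = 3.12, p = 0.026.
- 5.1 with SD 4.4: 5.1/1.796 = 2.84, p = 0.036.
- 7.0 with 5.5 as an SE: 7.0/5.5 = 1.27, p = 0.26.

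The p<0.05 in 1.4 favours reading 5.5 as an SD. It fits both SD pairs, so it does not choose between them.

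**4. Effect of the count.** 36 × 0.85 = 30.6 completers. 30 × 0.85 = 25.5, so 25 or 26. Two-sided detectable difference (mmHg):

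| Completers | SD 4.4 | SD 5.5 |
|---|---|---|
| 36 | 2.11 | 2.64 |
| 30 | 2.33 | 2.91 |
| 26 | 2.52 | 3.14 |
| 25 | 2.57 | 3.21 |

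Against 2.33, the range runs from 2.11/2.33 = 0.91 (9% better) to 3.21/2.33 = 1.38 (38% worse). The 25 to 26 count is a lower bound for some contrasts, because a patient who leaves in the last period may still contribute one pair.

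**5. Power for a 5.1 reduction (two-sided).** SD 5.5: 99.3% with 25 completers, 99.5% with 26, 99.8% with 30. SD 4.4: above 99.9% with 25 or more.

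**6. High versus low dose.** The recordings described compare on-drug with pre-treatment, at doses above the trial's low dose of 300 mg/day. They give no dose-versus-dose effect or SD. As illustration only: if that paired SD lay between 4.4 and 5.5, the detectable difference between doses would be 2.3 to 2.9 mmHg with 30 completers and 2.1 to 2.6 with 36.

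**The case against.** - **The two pairs may be different things.** 7.0±5.5 is stated for 600 mg/day, the six patients in 1.4 took 450 to 600 mg/day, and 5.1 is described as BP fluctuation. They could be different subsets or measures, and Fig. 4 might explain it. This stands: a reader might infer that 4.4 is wrong and 5.5 right, but the documents do not show that. The point is a missing link and missing labels.
- **± could be an SE.** Section 1.4 gives age as 18±2 with range 15 to 28 in six patients. With both extremes present and a mean that rounds to 18, the SD is at least about 4.7, and 4.7/√6 = 1.9, so ± there fits an SE. If 5.5 were an SE, the SD would be 5.5 × √6 = 13.5, the two-sided detectable difference with 30 completers would be 7.1, and power for 5.1 would be 52%. The p-value check makes this less plausible, but the section should say which it is.
- **Enrolled and randomised are different counts.** Section 6 puts enrolment before randomisation, so 36 enrolled and 30 randomised can both be true. This stands against calling 4.3 a contradiction; only the Overview in 1.4 conflicts outright. But 30 randomised still leaves no room for later dropout if 30 completers are wanted. Section 4.4.1 expects no retention problem, which sits awkwardly with the 15% in 7.2.
- **The null does not contradict the heading.** A paired high-minus-low test also has a null of no reduction. This stands. The mismatch is with the 5.1 benchmark and the absence of dose-versus-dose data.
- **Sample size may be revisited.** Section 8.6.1 foresees new power analyses after the interim, but possibly only if doses are modified. That does not repair the present text.

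**Conclusion.** The point holds in this form and should be fixed. The arithmetic in 7.2 is correct. Three things are not secured: the SD behind Table 3, the number to be enrolled and randomised, and the claim that the dose comparison is well powered. The stated two-sided sensitivity of 2.3 mmHg depends on SD 4.4 with about 30 completers. It is not reached with 25 to 26 completers, nor at SD 5.5 with 36 or fewer.

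Two stronger readings should be resisted. A reader might infer that the trial is underpowered for the drug effect. The figures do not show that, since power for 5.1 is 99% or more for a paired SD of 4.4 to 5.5 with 25 or more completers. A reader might equally infer that the placebo comparison is safe. That is not shown either: 5.1 is uncontrolled, appears to come from six patients, and says nothing about 300 mg/day versus placebo.

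Assumptions: 5.5 is an SD of paired differences wherever it is used as one, and dropout is 15%. The dose-comparison range is illustrative only.

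**What to change.** 1. **Preliminary figures.** Check 7.0±5.5, 4.4 and 5.1 against source data. Label each with its measure, number of patients, dose, and SD or SE. Keep Table 3 if 4.4 is confirmed for SD of daytime SBP. Otherwise recompute it with the confirmed paired SD. If that is 5.5, the one-/two-sided entries are 3.2/3.6 (n=20), 2.6/2.9 (n=30) and 2.2/2.5 (n=40).
2. **Counts.** State one enrolled number, one randomised number and one completer target throughout. If 36 are randomised for about 30 completers, correct 1.4 and 4.3 and label the 30 in the synopsis and 1.1. If 30 are randomised, correct 7.2 and restate the two-sided detectable difference for 25 to 26 completers (2.5 to 2.6 mmHg at SD 4.4, 3.1 to 3.2 at SD 5.5). The documents do not settle which was intended.
3. **Table 3 and 1.1.** Head the table with the contrast actually calculated. Either give a high-versus-low detectable difference with its assumed SD, or drop the claim that this comparison is well powered.

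Cost: one check of existing data and wording changes in the sections named. No patients are needed beyond the 36 already in 7.2, although which count is approved has to be confirmed first. The downside is that the stated detectable difference may become less favourable.

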A data and safety monitoring board (DSMB, Chaired by [name]) will review safety data on an ongoing basis. The study will continue until the target number of patients is enrolled or the DSMB recommends stopping the trial. To allow for a flexible trial design, there will be an interim efficacy analysis with access to the un-blinded after the first 15 patients have completed the trial. If carbidopa is found to significantly reduce blood pressure variability and the 300 mg/day (low-dose) is found to be equivalently effective as the 600mg/day (high-dose), we will decide, with the DSMB, whether to amend the protocol to add an additional treatment arm to test doses lower than 300 mg/day. Alternatively, if there is insufficient evidence to suggest that 600 mg/day of carbidopa reduces blood pressure variability, before terminating the trial for futility, we will drop the ineffective arms and collect exploratory data to explore the effectiveness of higher carbidopa doses up to 900 mg/day (for 28 days). We will modify the trial to include a titration from upwards of 600 mg/day in increments of 50 mg/day increases per week. To monitor safety closely, we will collect additional safety bloods (CBC and metabolic panel), 12 lead ECG and conduct comprehensive neurological examinations with each incremental titration step up and patients will be contacted by interim phone-calls to monitor adverse events. Only patients that live within 2-hours of the Dysautonomia Center will be included in the subsection to explore the efficacy of higher carbidopa dosages. We will conduct new power analyzes with the accumulated data and revise the sample size accordingly. Final analysis will be performed after the final study patient has completed the trial and the study is closed for enrollment. All end-points will be first examined using descriptive statistics. Each patient will serve as their own control allowing paired comparisons to be made between high-dose, low-dose and placebo data.

9 Data Handling and Record Keeping

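### The rule for switching from the t-test to Wilcoxon inspects raw daytime SBP SD, although the paired test depends on the shape of the within-patient differences

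*Combined protocol and SAP*

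**What the plan says.** Section 7.2 (Statistical Methods) states: "We will examine the sample distribution of SD of daytime SBP, and if it deviates from the normal distribution, we will employ" a Wilcoxon test. The sentence ends "we will employ the nonparametric Wilcoxon test for robustness", without saying whether the signed-rank or the rank-sum test is meant. The synopsis carries the same rule under Statistical Methodology. No normality test or threshold is given in either place.

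The test that the rule would displace appears in the power calculation of the same section, which is built on a within-patient quantity: "with an estimated standard deviation of 4.4 for the difference in SD". The test named there is a t-test of the one-sample kind at 0.05, in one-sided and two-sided form, and 20 patients are said to give 80% power for reductions of 2.5 and 2.9 mmHg respectively. Section 8.6.1 confirms the within-patient analysis: "Each patient will serve as their own control allowing paired comparisons to be made between high-dose, low-dose and placebo data".

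Section 7.2 also mentions ANOVA and ANCOVA for the repeated measures, to allow for covariates. Nowhere do the documents say that the differences, or the residuals of any model, will be inspected.

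**The concern.** A one-sample t-test on differences assumes that the differences are approximately normal. It assumes nothing about the values in each treatment period. Section 7.2 checks those period values.

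The two shapes can part company because pairing removes each patient's own level. Write a patient's value in a period as a personal level plus a treatment effect plus period-specific error. The personal level enters the raw distribution in full and cancels from the difference. A skewed spread of personal levels makes the raw values look non-normal even when the differences are well behaved. A wide normal spread can hide heavy-tailed differences.

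So the rule can err in both directions: discard the t-test when it is adequate, or keep it when the signed-rank test would be more efficient. At stake are some power and the clarity of which primary p-value the plan produces.

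**Working it through.** **1. Inputs.** From section 7.2: SD of the within-patient difference 4.4 mmHg, alpha 0.05, 80% power, one-sample t-test. The target is 30 patients ("we will choose a sample size of 30 patients"), with this allowance for loss: "To account for a drop out rate of around 15%, we will enroll 36 patients in the trial". Table 3 gives a two-sided detectable difference of 2.3 mmHg at n = 30.

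**2. The plan's own figures.** Two-sided power is P(|T| > t(1 − α/2, n − 1)), where T is noncentral t with n − 1 df and noncentrality √n × Δ/σ. At n = 30 and Δ = 2.3 the noncentrality is 5.477 × 2.3/4.4 = 2.86, and power is 79.0%. Solving for 80% power (one-sided / two-sided):

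| n | Recomputed | Table 3 |
|---|---|---|
| 20 | 2.54 / 2.91 | 2.5 / 2.9 |
| 30 | 2.05 / 2.33 | 2.0 / 2.3 |
| 40 | 1.76 / 2.00 | 1.8 / 2.0 |

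For dropout, 30/0.85 = 35.3, which rounds up to 36. The sizing reproduces, and it rests on the differences.

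**3. Why the raw check sees little of the differences.** In the simulations below each patient has a base value, and the two period values are base ± d/2, where d is the difference. With an assumed base SD of 6, the raw variance is 6² + 4.4²/4 = 36 + 4.84 = 40.84. The differences contribute 4.84/40.84 = 12% of it.

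**4. Simulation.** Settings: 6,000 trials per scenario, n = 30, two-sided 0.05, difference SD 4.4, reduction 2.3. The documents give no criterion and no distributional data, so two things are assumed: Shapiro-Wilk at 0.05 as the check (in either period for the raw rule), and the shapes in the table. The Monte Carlo standard error is √(0.79 × 0.21/6000) = 0.5 points for power.

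| Differences; raw values | Wilcoxon chosen: raw rule / difference rule | Power: raw rule | Power: difference rule | Power: t always | Power: Wilcoxon always |
|---|---|---|---|---|---|
| Normal; base 15 + exponential, mean 6 | 84% / 5% | 76.9% | 78.2% | 78.2% | 76.5% |
| t, 3 df; base normal | 12% / 46% | 86.4% | 93.3% | 84.3% | 94.1% |
| Laplace; base normal | 10% / 36% | 79.8% | 85.0% | 79.0% | 87.3% |

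Losses from using the raw rule instead of the difference rule: 78.2 − 76.9 = 1.3, 93.3 − 86.4 = 6.9 and 85.0 − 79.8 = 5.2 points. With no true effect, rejection under either rule was 4.6% to 5.1% in these three scenarios.

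A second simulation gave 75.8% against 77.6%, 86.5% against 93.7% and 80.8% against 85.4%. Those losses are 1.8, 7.2 and 4.6 points.

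**5. Shapes built from the measurement.** The ambulatory monitoring instructions call for a reading every 30 minutes. Assuming 16 waking hours, that is 16 × 2 = 32 daytime readings. When each daytime SD is computed from about 32 simulated readings (true SD assumed near 20), the difference SD comes out at 4.3 to 4.4, close to the plan's 4.4. Power under the raw and difference rules was then 79.6% and 79.8% in one set of runs, and 78.1% and 78.3% in another. With readings skewed to the right to mimic hypertensive surges it was 64.8% under both rules. The gap disappears.

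**6. Limits of moving the check.** With strongly skewed differences (centred exponential) and normal base values, rejection at zero mean difference was 8.4% under the raw rule and 15.8% under the difference rule. The signed-rank test relies on symmetry, and here the difference rule chose it in 97% of trials. Re-aiming the check while still letting it choose the test is only a partial repair.

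**The case against.** The wording may be shorthand. Section 7.2 defines the primary outcome as a reduction, sizes the trial on the difference in SD and names a one-sample test, so the authors may have meant to inspect the change. That is possible, but the section uses separate terms for the measure and for its change, and the rule names the measure. If the change was meant, the text should say so.

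The cost also depends on assumptions. No figure in the documents supports heavy-tailed differences, and the switching rates depend on an imposed Shapiro-Wilk rule. Even with t (3 df) differences the stated rule keeps about 86% power, above the 80% target. The effect used is the minimum detectable one; section 7.2 cites observed reductions of 5.1 and 7.0 mmHg, at which the choice of test would matter less. A needless switch to a valid test is nearly harmless. All of this stands, and it limits the size of the point. It does not make the raw values the right thing to inspect.

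Two stronger readings are tempting. A reader might infer that the entry criterion of systolic SD above 15 mmHg distorts the raw distribution. It is one of three alternative routes in section 4.1, and section 7.2 says 99% of FD patients meet the criteria, so the documents do not support that mechanism. A reader might also infer that a normal-theory mixed model would recover the lost power. Under t (3 df) differences the t-test, used as a proxy for that model, gave 84.8% against 86.5% for the stated rule, so it would do slightly worse.

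**Conclusion.** The stated rule inspects the wrong quantity, and this is a minor point. The mismatch follows from the text alone: a paired test, sized on differences, is chosen or dropped according to the shape of unpaired values.

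The size rests on assumed distributions and an assumed normality check. A needless switch costs about 1 to 2 points of power. A missed switch costs about 5 to 7 points if the differences are Laplace or t with 3 df, and essentially nothing in simulations built from about 32 daytime readings.

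A reader might infer that the trial is undersized or its error rate inflated by this rule. Neither follows. The sample size does not depend on it, and type I error stays near 5% when the differences are symmetric. Strong skew is a separate hazard, which checking the differences does not cure. Nor should the gap between the stated rule and Wilcoxon throughout (86.4% against 94.1% under t, 3 df) be quoted as the cost of inspecting raw values; the like-for-like comparison is with the same rule applied to the differences.

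**What to change.** In section 7.2 and the synopsis, replace the check on raw daytime SBP SD with an inspection of the paired treatment differences, or of the residuals if a crossover model is used. Name the Wilcoxon test as the signed-rank test on paired differences. Fix one primary test in advance, and report the other as a set sensitivity analysis whatever the inspection shows, so that the inspection informs interpretation and does not choose the test. The choice should be recorded before the unblinded interim look described in section 8.6.1.

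The cost is about two sentences in each place, with no change to data collection or sample size.

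Either choice has a price. A normal-theory primary test loses power to the signed-rank test if the differences are heavy-tailed: 84.3% against 94.1% under t (3 df), and 79.0% against 87.3% under Laplace. A signed-rank primary test gives up 78.2 − 76.5 = 1.7 points if the differences are normal, and it relies on their symmetry. The case for the change is that the right quantity is inspected and the test is settled beforehand, not that a particular model gains power.

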Patients will be screened for eligibility and enrolled in the trial. Informed consent or ascent will be obtained. Patients will be given a tutorial and provided with written instructions on using the ambulatory blood pressure monitors and 24-h recordings will be obtained. Supine/sitting/standing office blood pressures will be measured. RR-interval and beat-to-beat blood pressure will be recorded for 5 minutes before and during a Stroop test (3-minutes) and during serial 7 subtractions (3 minutes). Patients will be asked to rate their symptoms of orthostatic hypotension on the validated orthostatic hypotension-questionnaire (OH-Q)⁴². Baseline safety bloods (CBC & metabolic panel), a 12-lead ECG and a physical and neurological exam will be obtained. After completing all baseline measures, patients will be randomized to the treatment order sequence (Fig. 6) in a 1:1:1 ratio. For patients that opt to continue follow-up via 2-way telemedicine conferencing, investigators will ensure that the patient has access to a validated blood pressure and heart rate monitor, weighing scale and thermometer at home. These will be provided, if needed. Patients will be given a continuous, automatic, wireless wrist-based heart rate tracker (Fitbit Charge HR, Fitbit, USA), which will be synchronized to allow remote monitoring at the Center. Patients and caregivers will be trained in how to perform a timed active stand test and to obtain blood pressure and heart rate supine (5-min), seated (2-min) and standing (5 min). Written instructions and a video guide will be provided.

Before leaving the office, patients will be instructed to keep a daily symptom diary (a modified version of the Rhodes Nausea/Retching/Vomiting Index³⁹ with additional space to note adverse events). Additionally, patients will be told to contact the Center to report any adverse event. They will be contacted by phone call on the day that they adjust their dose. Seven-days into their treatment arm patients will be contacted again to monitor tolerability and adverse events. Thereafter, we will contact patients on a weekly basis to monitor potential adverse events. They will return for the next study visit in 28-days.

Patients that have been seen at the Center within the last 3-months may have the option of completing the study screening and enrollment proceedures via virtual visits, at the discretion of the PI (a treating investigator).

Visit 2. Crossover #1:

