7.3 Subject Population(s) for Analysis

- All-treated population: Any subject randomized into the study that received at least one dose of study drug
- Protocol-compliant population: Any subject who was randomized and received the protocol required study drug exposure and required protocol processing

8 Safety and Adverse Events

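### The three-period crossover analysis does not commit to a period term, so a period effect would cost power for small contrasts and, with unequal completers, bias the paired estimates

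*Combined protocol and SAP*

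**What the plan says.** **Design.** The Overview in Section 1.4 states that "enrolled patients will be randomly assigned to one of three treatment sequences": high/low/placebo (HLP), low/placebo/high (LPH) or placebo/high/low (PHL). Section 6, Visit 1 adds that "patients will be randomized to the treatment order sequence (Fig. 6) in a 1:1:1 ratio". Each treatment therefore appears once in each period.

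**Analysis.** Section 7.2 calculates power "at a significance level of 0.05 using a one-sided (or two-sided) one-sample t-test", and Table 3 is headed "Minimal detectable difference: SD BP variability high vs. low dose". For the data analysis, Section 7.2 looks at the distribution of the daytime systolic SD and says "if it deviates from the normal distribution, we will employ the nonparametric Wilcoxon test for robustness", without a criterion for deviation. For the repeated measurements it then states: "to account for potential covariates, such as age, gender, and disease severity, the analysis of (co)variance (ANOVA and ANCOVA) methods will be used". Section 8.6.1 adds: "Each patient will serve as their own control allowing paired comparisons to be made between high-dose, low-dose and placebo data".

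**Populations.** The all-treated population in Section 7.3 is "Any subject randomized into the study that received at least one dose of study drug". Section 7.2 allows for about 15% dropout by enrolling 36 patients to obtain 30.

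Neither period nor sequence is named as an analysis term anywhere. Section 1.5 discusses carryover and the 2-day washout, which is a different matter.

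**The concern.** In a crossover, a within-patient difference removes whatever is constant within the patient. Age, gender and disease severity are constant over 14 weeks, so adjusting for them does nothing for a complete paired contrast. Period is not constant. Two treatments are always compared across two different periods, and which two depends on the sequence. A shift over calendar time, or from growing used to repeated monitoring, therefore enters each patient's difference with a size and sign set by the sequence.

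This has two consequences. With equal sequences the shifts average to zero, but they inflate the variance of the differences, so the test becomes conservative and loses power. With unequal completers they no longer average to zero, and the estimate is biased in a direction that depends on who left.

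The contrasts at risk are the small ones. Aim 3 is dose finding, Table 3 is framed as high versus low dose, and the interim look in Section 8.6.1 asks whether the low dose is as effective as the high dose. In that setting, lost precision can be mistaken for similarity.

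Paired tests also drop any patient who lacks one of the two periods compared, although the all-treated population includes such patients. And the choice between t-test and Wilcoxon is made after seeing the data.

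**Working it through.** **1. Reproducing Table 3.** Inputs from Section 7.2: difference SD 4.4 mmHg, alpha 0.05, 80% power, one-sample t-test. Solving the noncentral t distribution with n-1 degrees of freedom gives these detectable differences (one-/two-sided):

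| n | Recomputed | Table 3 |
|---|---|---|
| 20 | 2.54 / 2.91 | 2.5 / 2.9 |
| 30 | 2.05 / 2.33 | 2.0 / 2.3 |
| 40 | 1.76 / 2.00 | 1.8 / 2.0 |

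The table is reproduced, and 30/(1-0.15) rounds up to 36. These figures assume that no period variation enters the difference.

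**2. How period enters high minus placebo.** With period levels p1, p2, p3, the contribution is p1-p3 in HLP, p3-p2 in LPH and p2-p1 in PHL. These sum to zero. The shifts below are assumptions, since the documents give none. The inflated SD for 10/10/10 completers is √(4.4² + 10 × sum of squares / 29).

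| Assumed shift (mmHg) | HLP / LPH / PHL | Inflated SD |
|---|---|---|
| 0/-1/-1.5 | +1.5 / -0.5 / -1.0 | √(19.36 + 35/29) = 4.54 |
| 0/-2/-3 | +3 / -1 / -2 | √(19.36 + 140/29) = 4.92 |
| 0/-3/-5 | +5 / -2 / -3 | √(19.36 + 380/29) = 5.70 |

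High minus low has the same three absolute values in another order, so the inflation is identical.

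**3. Power at 2.33 mmHg, 10/10/10, two-sided 5%.** Crossovers were simulated (at least 10,000 per scenario) with within-patient SD 4.4/√2. The paired t-test was compared with least squares on patient, period and treatment (90-30-2-2 = 56 df). Ranges cover repeated runs and both contrasts.

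| Shift | Paired | With period |
|---|---|---|
| none | 80–81% | 81–82% |
| 0/-1/-1.5 | 78–79% | 81–82% |
| 0/-2/-3 | 72–73% | 81–82% |
| 0/-3/-5 | 60–61% | 81–82% |

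Paired type I error falls from about 5% to about 3% (0/-2/-3) and 1–1.5% (0/-3/-5). At 5.1 mmHg paired power stays above 99%.

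**4. ANOVA without period does not help.** Under a linear drift of d per period, high minus low picks up d, -2d and d, which adds about 2d² to the variance. At 2.3 mmHg, power is 67% (d=2) and 51% (d=3) for the paired test, 69% and 53% for repeated-measures ANOVA without period, and about 81% with period.

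**5. Unequal completers, high minus placebo, shift 0/-2/-3.** Bias is the completer-weighted mean of +3, -1 and -2, with completers in the order HLP/LPH/PHL.
- 12/12/6: (36-12-12)/30 = +0.4 mmHg, against carbidopa; type I error about 5%.
- 6/12/12: (18-12-24)/30 = -0.6 mmHg, towards carbidopa; type I error 8–9%.
- Random loss of six from 12/12/12: median absolute bias 0.13 mmHg, 95th percentile 0.30.

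The period-adjusted estimate is unbiased in each case.

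**6. Dropout by period.** Assume three of 36 leave after period 1 and three after period 2. Leaving after period 2 removes the high–placebo pair in HLP and LPH but not in PHL, so expected pairs are 10/10/11. Mean bias is (30-10-22)/31 = -0.06 mmHg for 0/-2/-3 and (50-20-33)/31 = -0.10 for 0/-3/-5, even with random dropout. Power, paired versus adjusted using all available periods, is 82% versus 84% with no shift, 77% versus 84% for 0/-2/-3 and 67% versus 84% for 0/-3/-5.

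**The case against.** The strongest reply is that the harm rests on a period effect that no document reports. At the mildest assumed shift the loss is about two points of power. The large loss needs a drift about as big as the 5.1 mmHg treatment effect, in recordings already standardized for start time and cuff size. Section 7.2 also gives 7.0±5.5 mmHg for the preliminary reduction. If 5.5 is the SD of the difference (an assumption), paired power at that SD's own detectable difference of 2.9 mmHg falls from 80% to 75% (0/-2/-3) or 67–68% (0/-3/-5), a smaller drop. This all stands, and it makes the finding conditional.

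The design also balances period: Section 4.3 uses permuted blocks, and Section 4.4.1 expects no retention problem. Losing all six patients from one given sequence has probability of about 0.05% under random dropout. This stands too. The +0.4 and -0.6 mmHg figures are worst cases, and bias is the lesser part of the concern.

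Finally, the covariate list is open, so period could be added without contradicting the plan, and enrolling 36 already covers lost pairs. Both are true, but permission is not pre-specification. Over-enrolment restores the number of pairs. It does not remove period variance or correct an imbalance between sequences. Part of the model's small advantage with no shift comes from pooled error and retained data, not from the period term.

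**Conclusion.** The concern holds. Period is not pre-specified in a three-period crossover, and the named covariates cannot stand in for it. If period shifts the outcome by 0/-2/-3 mmHg, paired power for a 2.33 mmHg contrast is about 73% instead of 81–82%; for 0/-3/-5 it is about 60%. With equal completers the paired test errs on the conservative side and is unbiased. With unequal completers it is biased, typically by 0.1 to 0.3 mmHg under random dropout and 0/-2/-3, and by up to 0.6 mmHg in the one-sequence cases examined.

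These figures rest on assumed shifts and on a difference SD of 4.4 mmHg that contains no period variation. With no period effect there is no harm, and an effect of 5.1 mmHg is safe either way. The exposed comparison is high versus low dose. The change should be made because it improves the analysis at no cost in power. The uncontrolled choice between t-test and Wilcoxon is a related gap, but these figures do not measure it.

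**What to change.** Name one primary analysis of daytime systolic SD in Section 7.2:

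- A linear mixed model with fixed effects for treatment and period (sequence optional) and a random patient effect.
- All treated patients with at least one on-treatment recording, analysed by the treatment and period of each recording.
- Three stated contrasts: high minus placebo, low minus placebo and high minus low.
- Age, gender and disease severity left out of the primary model and kept for sensitivity or interaction analyses.
- The outcome scale (raw or log SD) fixed before unblinding.
- The Wilcoxon test on within-patient differences kept as a sensitivity analysis, not as a replacement triggered by the data.

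The cost is SAP wording and a standard model. No new data are needed. Period takes two degrees of freedom (58 to 56 with 30 complete patients), and simulated power with no period shift is no lower than that of the paired test.
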